### DURABLE - 1st Procedure

[figure not shown]

Figure 1: Step-by-step 1st procedure, using both CARTO3 and D700 interchangeably.

■ **Second AF ablation procedure (Figure 2):**

- The second procedure will be conducted 1 month after the initial procedure in a similar set up under CARTO3 guidance.
- After repeated registration, with the previous pre-acquired 3D image, the LA will be remapped.
- In order to functionally identify existing gaps, remaining gaps will be sought for by electrical functional test.

MASTER

- If such gaps will be encountered, the physician will apply the customary touch-up approach.
- The location of gaps around the PVs will be reported in 8-16 segments (Figure 3).

## **DURABLE – I, 2nd Procedure**

[figure not shown]
[figure not shown]

Figure 2: Step-by-step 2nd procedure, gap detection and re-isolation.

**Figure 3: Data collection around PVs.** (A) Data collection at 8 numbered sections: 1, 9 – superior; 2, 16 – anterior superior; 3, 15 – anterior middle; 4, 14 – anterior inferior; 5, 13 – inferior; 6, 12 – posterior inferior; 7, 11 – posterior middle; 8, 10 – posterior

superior; (B) Sections 2, 3, 4 and 14, 15, 16 were grouped, respectively, into left and right anterior segments and 6, 7, 8 and 10, 11, 12 were grouped, respectively, into left and right posterior segments.

**Data to be collected during the procedures:**

- Overall procedure time.
- Overall EPD D700 set up time.
- Fluoroscopy time.
- Acute (during and immediately after the procedure) AE/SAE Evaluation.
- Full CARTO3 location data (CARTO3 export file).
- Full CARTO3 Point List and Tags.
- Pre-ablation, during and Immediate Post-ablation lesion assessment at each ablation point.
- Each ablation site location will be tagged on both CARTO3 and EPD D700 maps.
- As SmartTouch® is used, contact force data will also be recorded.
- Recording system data.

*This document was created using  
Solid PDF Tools  
http://www.SolidDocuments.com/  
To remove this message, purchase the product at*

MASTER

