## DURABLE-I STUDY:

### DIELECTRIC UNRAVELLING OF RADIOFREQUENCY ABLATION EFFECTIVENESS

#### Study Purpose

The purpose of this study is to evaluate real-time gap detection using EPD D700 dielectric sensing compared with customary electrical isolation tests and Adenosine infusion at the end of the procedure. Furthermore, safety, usability and clinical applicability of the system for guided AF ablation will be confirmed.

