#### Study Design

Prospective, single-center, non-randomized, non-blinded, open label, and single arm study.

All procedures will be performed under CARTO 3 guidance for the treatment of atrial fibrillation (AF). The EPD D700 system will be used interchangeably, to record pre-, during and immediate post-ablation tissue characteristics and compute likelihood of lesion transmurality and permanency. Additionally, D700 system safety, feasibility, usability and clinical applicability will be documented.

The entire procedure will be conducted as customary, using standard and approved off-the-shelf equipment (body surface electrodes, diagnostic and irrigated ablation catheters, RF generator and recording system), in a completely clinically independent manner from the EPD D700 system. The physician will neither use nor rely on any of the D700 system output for clinical decision making and will be blinded to the D700 lesion assessment forecasts. One month following the initial procedure, a repeated procedure will be performed for gap detection and its results will be correlated with the D700 predictions.

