#### Study Population

Twenty-four Paroxysmal Atrial-Fibrillation (PAF) patients, amenable to catheter-based AF ablation therapy comprising of Pulmonary Veins Isolation (PVI). We suggest that 4 will patients decline to participate. The overall number of patients in the study is twenty.

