## Key Exclusion Criteria

1. Any planned surgical or endovascular intervention within 30 days before or after the index procedures.
2. Subject is enrolled in another drug or device study protocol that has not reached its primary endpoint.
3. Previous AF ablation therapy.
4. Clinical evidence of active coronary ischemia, significant Valvular heart disease, or hemodynamically significant congenital cardiac abnormality.
5. Patient had experienced myocardial infarction (MI), stroke (CVA) or transient ischemic attack (TIA) or other neurological disturbances.
6. Patient has a pacemaker.
7. Thrombi detected in the heart.
8. Life expectancy less than 12 months.
9. Known severe renal insufficiency.
10. Known allergy to Iodine.

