## Study procedures

- **Cardiac CT (pre-procedure imaging) or MR.**
- **CT/MR post-processing and analysis at EPD Research (Caesarea, Israel):**
  - **Cardiac chambers' segmentation**
  - **Electrical fields computation**
  - **Optional recommended PVI ablation lines**
  - **Optional preliminary lesion forecast at the point level**
- **Forwarding the ready to use pre-planned data to the site.**
- **First AF ablation procedure (Figure 1):**
  - EPD D700 system installed in the EP cath-lab.
  - Deployment of body surface electrodes (patches) by the local EP technician/nurse under supervision of EPD Research team members, to be used later by both the CARTO3 and EPD D700 system, interchangeably, according to the diagrams in Appendix 1.
  - Deployment of BWI body surface magnetic sensors according to the customary setup guidelines.
  - Connecting the ThermoCool SmartTouch ablation catheter via the commercially available extension cables to the CARTO3 system according to the diagrams in Appendix 1.
  - Connecting the Stockert RF ablation generator to the CARTO3 system according to the diagrams in Appendix 1.
  - Registration of the pre-acquired 3D CT or MR images of the Right Atrium (RA) with EPD D700, using CARTOMERGE module.
  - Registration of the pre-acquired 3D CT or MR images of the RA with EPD D700 system under fluoroscopy and or CARTO3-guidance.
  - Performance of Transseptal Procedure under fluoroscopy and/or ultrasound (TEE or ICE) guidance.
  - Registration of the pre-acquired 3D CT or MR images of the Left Atrium (LA) and Pulmonary Veins (PVs) with CARTO3 using CARTOMERGE module.
  - Registration of the pre-acquired 3D CT or MR images of the LA and PVs with EPD D700 system under fluoroscopy or CARTO3-guidance.
  - Targeted navigation inside the LA and reaching the 1st, either user-determined or computer recommended, point of the 1st preplanned PVI ablation lines.
  - Performing the specific ablation strategy while ascertaining contiguity using VisiTAG module, i.e. 5-6 mm between consecutive ablation points, and moving along the PVI line systematically in preplanned continuous order. The specific ablation parameters to be used, i.e. 30 W 30 and 25W a30 sec in anterior and posterior LA wall, respectively; as well as the desired Ablation Index to be reached, will be determined solely by the operator regardless of the system's recommendation.

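### AE/SAE collection stops at the immediate post-procedure period of each procedure, while the plan says that safety will be confirmed

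*Combined protocol and SAP*

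**What the plan says.** Study Purpose puts gap detection first and then adds that "safety, usability and clinical applicability of the system for guided AF ablation will be confirmed". Study Design uses a weaker verb for the same aim: "D700 system safety, feasibility, usability and clinical applicability will be documented". Neither section attaches a safety endpoint, an acceptance criterion or an observation period.

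The one AE/SAE item is in the list headed Data to be collected during the procedures: "Acute (during and immediately after the procedure) AE/SAE Evaluation". The heading is plural, so the item covers both procedures. The length of the immediate period is not given in hours or days.

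On the second procedure, Study Design says: "One month following the initial procedure, a repeated procedure will be performed for gap detection". The section on the second AF ablation procedure allows touch-up ablation if gaps are found. Baseline Assessment and Study procedures describe no visit, contact or adverse-event enquiry between the procedures, or later than the immediate period after the second. The figures for the two procedures could not be read, but their captions describe procedural steps.

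On sample size, Study Population says: "The overall number of patients in the study is twenty".

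**The concern.** The safety aim is wider than the data meant to support it. An event that arises days or weeks after the first ablation, or after the patient has left the immediate care of the second, has no specified route into the study data. If the plan is followed as written, such events could be missed and safety could still be reported as confirmed.

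Two features of the design make this matter. First, the repeat procedure is done for the study's own purpose, so what follows it belongs in the study's safety record. Second, the D700 is not merely an observer. According to Appendix 1, in D700 mode the RF generator and the body surface patches are switched to the D700 through the connection boxes, and RF energy reaches the catheter tip through a filter that blocks the D700 frequencies. The Available Modes table states in advance that ablation in this mode is safe and adds no new risk. That is an assertion, and acute data alone cannot test it for later events.

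**Working it through.** **1. The plan's own figure.** Study Population starts from 24 patients and expects 4 to decline: 24 − 4 = 20. This reproduces. The plan states no safety event rate, threshold or precision, so there is no safety calculation to reproduce.

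**2. Coverage of AE/SAE collection, period by period.**

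| Period | AE/SAE collection specified? |
|---|---|
| During and immediately after the first procedure | Yes, length undefined |
| Rest of the month to the second procedure | No |
| During and immediately after the second procedure | Yes, length undefined |
| Beyond the immediate period after the second | No |

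**3. What the two uncovered periods could hold (illustration only).** Let q be a patient's risk of at least one event in the uncovered periods. The documents give no value, so q is assumed, and patients are taken as independent. With n = 20:

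- Chance that at least one patient has such an event: 1 − (1 − q)^20.
- Expected number of patients with such an event: 20q.

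| Assumed q | 1 − (1 − q)^20 | 20q |
|---|---|---|
| 2% | 1 − 0.98^20 = 33% | 0.4 |
| 5% | 1 − 0.95^20 = 64% | 1.0 |
| 10% | 1 − 0.90^20 = 88% | 2.0 |

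The chance reaches 50% when q = 1 − 0.5^(1/20) = 3.4%. The result depends on what counts as an event: q for any AE will be at least as high as q for an SAE.

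**4. The word *confirmed*, taken separately.** With 0 events in 20 patients, the exact two-sided 95% upper limit is 1 − 0.025^(1/20) = 16.8%. This limit comes from the sample size. Lengthening the window would not change it, and it does not measure the gap shown in step 2. It shows only that 20 single-arm patients without a criterion can support a description of safety and not a confirmation.

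**The case against.** The strongest reply is that the safety aim concerns the D700 and not ablation in general. The system is in use only during the procedures, and "The physician will neither use nor rely on any of the D700 system output for clinical decision making". The Available Modes table adds that RF energy transfer is not degraded. On that view an acute window matches the exposure. With one arm and no comparator, later events could not be attributed to the D700 as distinct from customary ablation.

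The attribution point stands: wider collection would describe what happened to the patients and would not isolate a device effect. But leaving treatment decisions untouched does not make the acute window sufficient, because the system switches the RF and patch connections and the repeat procedure is study-driven. The statement of no new risk is what safety data should examine, so it cannot justify not collecting them.

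It is also fair to say that an acute item fits a list of data collected during procedures. The quoted line is not wrong in itself. The fault is that nothing elsewhere covers the later periods.

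The text does not support four stronger readings that a reader might infer:

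- *Nothing is collected after the second procedure.* The plural heading covers its immediate aftermath.
- *Later reporting is ruled out.* The plan does not forbid it. It only fails to call for it.
- *A 30-day safety follow-up is implied.* The only 30-day period in the text is an eligibility rule: "Any planned surgical or endovascular intervention within 30 days before or after the index procedures". It gives no basis for an adverse-event period.
- *The 33%, 64% and 88% are estimates of missed harm.* They follow from assumed risks and have no source in the documents.

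**Conclusion.** The point holds for a limited claim. AE/SAE collection is specified only for an acute period of undefined length around each procedure. Nothing is specified for the rest of the interval or for later events after the second procedure. The two statements of the safety aim differ in strength, and neither has a criterion. A safety statement built on these data would cover acute events only, and *confirmed* is stronger than the design supports.

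The size of the loss cannot be fixed from the documents. It rests on an assumed later-event risk and on independence between patients, and an uncollected event becomes more likely than not once that risk exceeds about 3.4% per patient. The finding that the later periods are uncovered rests on the readable text and on no assumed risk.

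Gap detection, the lead purpose, is unaffected. This is a cheap improvement to the safety record and does not threaten the main result.

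**What to change.** Keep the acute item where it is, and add a separate item outside the list for data collected during the procedures:

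> AE/SAE are collected from the first ablation procedure through the interval to the second, and for a period after the second that the sponsor sets. Events since the first procedure are asked for when the patient attends for the second, and events after the second are asked for at one routine contact. Acute and later events are reported separately.

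In Study Purpose, reconcile the safety aim with Study Design by replacing *confirmed* with *documented* for safety. State what will be reported: the number and proportion of patients with at least one SAE, and with at least one AE, each with exact 95% confidence limits.

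**Cost.** The interval enquiry uses an attendance that already takes place. The later enquiry needs about 20 brief contacts, one per patient, and the study runs slightly longer, until the last of these. More events may be reported, and the safety statement becomes weaker. Later events still cannot be attributed to the D700 as distinct from ablation, and the report should say so.

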## Appendix 1: CARTO3 and EPD D700 operating in-tandem

This appendix describes the connection between D700 system and CARTO3 (Biosense Webster JNJ) system that was especially developed in order to enable temporary operation of the two systems in-tandem. This is a requirement that must be met merely in the interim phase until users gain full confidence in D700's accuracy and reliability. The connection between the two systems is accomplished by two EPD external boxes:

- EPD CARTO3 Cat box
- EPD CARTO3 Patch box

There are two operational modes enabled while using these connection boxes:

- a. CARTO3 mode:

In this mode the CARTO3 is connected as stand-alone system and retains all its customary functionalities using both EM and Impedance-based localization.

- b. D700 mode:

In this mode the system toggles the RF generator and the body surface patches to the D700 system, while disconnecting the CARTO3 from the ablation catheter and the body surface patches. Dummy loads are connected to CARTO3 system as inputs. In this mode, although an error message might appear on CARTO3 screen, the CARTO3 is still using its magnetic location and the navigable catheters equipped with a magnetic sensor will still be visualized.

### D700 and CARTO3 connection - Top level

Figure 1 shows the connection between the two systems.

The control cable carries voltage and control signals for the internal relay box.

The connection is made by the two connection boxes:

#### EPD Cart3 Cat box

The EPD Cart3 Cat box is used to connect between the ablation catheter, RF generator, and the D700 system.

Figure 2 shows the internal connections when the box is set to CARTO3 standalone mode. In CARTO3 standalone mode the RF generator is connected directly to CARTO3 and the ablation catheter electrodes C4-C1 are connected directly to CARTO3. The relay position is set by a control signal from D700. All the relays are hi-voltage enabled and defibrillation safe.

Figure 3 shows the box in the D700 mode. The 13 KHz block filter is used to block the location signals of the D700 from the RF generator low impedance output.

Dummy resistors load are connected to CARTO3 inputs.

#### EPD Cart3 Patch box

The EPD Cart3 patches box is used to connect between the body surface patches to CARTO3 or D700 system, interchangeably.

Figure 4 shows the internal connections when the box is set to CARTO3 mode.  
Figure 5 shows the connection when the box is set to D700 mode.

## Available Modes

System Mode	Description	Note
CARTO3 only	The CARTO3 is connected to all catheter electrodes, body surface patches, and RF generator	Same full performance as standalone CARTO3 system, all indwelling catheters, including SmartTouch ablation catheter, Lasso and Decapolar diagnostic catheters, and all their electrodes will be visualized on the CARTO screen
D700 + CARTO3 in EM location only	1. The CARTO3 is connected only to electromagnetic and temperature sensors, hence the ablation catheter will still be correctly localized and displayed on the CARTO screen 2. Ablation catheter C4-C1 connected to D700, CARTO3 is optionally connected to dummy load 3. RF generator is connected to C1 with a blocking filter of D700 frequencies 4. Body surface patches are connected to D700 5. CARTO3 body surface input is optionally connected to dummy load	

• No RF performance degradation (energy transfer) in C1.

• ECG signals of C1 to C4 transferred to recording system from D700 RS connection box.

• Error message on CARTO screen due to "loss" of impedance input.

• Non-navigation diagnostic catheters, whose visualization solely depends on impedance measurements (body surface patches reading the current injected from the electrodes on the catheter), will temporarily disappear from the CARTO screen

• The intra-cardiac ECG will be displayed on the recording system in the channels reserved for D700 rather than the channels

		
reserved for the CARTO3
 

• Performing an ablation under this mode will be safe and there'll be no associated new risk to the patient

--	--	--

## Supported catheters

### CARTO®3

1. NAVISTAR catheter / THERMOCOOL® SF catheter
2. THERMOCOOL SMARTTOUCH® catheter
3. LASSO catheter

## External Cables used

### Therapeutic CARTO® 3 System Cables:

1. CR3425CT 3 m Cable for existing NAVSTAR® Catheter, 25 pin black, 34 pin red
2. CR3434CT 3 m Cable for THERMOCOOL SMARTTOUCH® Catheter, 34 pin red, 34 pin red
3. 39E43R PIU to Stockert EP Shuttle Generator

*To remove this message, purchase the product at  
Solid PDF Tools  
<http://www.SolidDocuments.com/>*

MASTER

[figure not shown]

Figure 1: D700 and CARTO3 connections

[figure not shown]

Figure 2: Cat box in CARTO3 mode

[figure not shown]

Figure 3: Cat box in D700 mode

MASTER

[figure not shown]

Figure 4: Patches box in CARTO3 mode

[figure not shown]

Figure 5: Patches box in D700 mode

This document was created using  
Solid PDF Tools  
To remove this message, purchase the product at  
<http://www.SolidDocuments.com/>
